All AEs will be coded using MedDRA version 24.0 or higher. A treatment-emergent AE (TEAE) is defined as any AE that occurs or worsens after initiation of study treatment.

The duration in days of each AE will be calculated as (resolution date of AE – onset date of AE + 1). For the determination of TEAEs and calculation of durations for AD flares, the following rules regarding partial dates will be applied:

- If only the day is missing for a start date, the 1st of the month will be imputed. If the new estimated date falls before the date of first dose, while the known month and year match the month and year of the first dose, the date of first dose will be used as the new estimated date. The AE will be considered as a TEAE.
- If only the day is missing for an end date, the last day of the month will be imputed. If the new estimated date falls after the date of last study visit, the date of last study visit will be used as the new estimated date.
- If both the day and the month are missing for a start date or end date, no imputation will be used, and the duration will not be calculated. However, if the year of start is the same or greater than the year of the first dose date, the AE will be considered as treatment emergent.

- If the start date or end date is completely missing, duration will not be calculated. However, an event with completely missing start date will be considered as treatment emergent.

An overall summary of AEs will be presented by treatment and overall. The summary will include the total number of events, frequency counts and percentages with:

- All AEs
- TEAEs
- Treatment-emergent Serious Adverse Events (SAEs)
- Treatment-related TEAEs
- Treatment-related treatment-emergent SAEs
- TEAEs leading to study drug discontinuation
- Injection site reactions
- AEs of Special Interest (AESIs): conjunctivitis, keratitis and other ophthalmic events evaluated by an ophthalmologist.

Summaries of the incidence of TEAEs will be displayed by treatment according to the following:

- All TEAEs by SOC in descending order of frequency (in the sequence of all subjects, all active treatments, CBP-201 3000 mg [300 mg Q2W] group) and PT in the same order of frequency
- All TEAEs by SOC, PT, and maximum severity (1 mild, 2 moderate, 3 severe, 4 life-threatening, 5 death)
- All TEAEs by SOC, PT, and maximum causality (not related, related) to study treatment
- All serious TEAEs by SOC and PT
- All AESI by SOC and PT

For these summaries, subjects with multiple AEs will be counted only once per SOC and PT.

All AEs will be presented in a by-treatment, and by-subject listing, detailing the verbatim term given by the investigator, the PT, SOC, onset date, end date, CTCAE grade, outcome, relationship to study treatment, action taken with study drug, other action taken, seriousness and criteria for seriousness. SAEs and AEs leading to study treatment discontinuation, and AESI will also be presented in a separate listing.

COVID-19 related adverse events may also be summarized separately if deemed necessary.

C. Clinical Laboratory Results

For continuous laboratory parameters, descriptive statistics will be presented for the value at each assessment time and for the changes from baseline labs by treatment group.

Additionally, clinical laboratory parameters will be categorized as low, normal, or high according to laboratory range specifications and the number and percentage of subjects in each category will be presented in shift tables.

Laboratory values that are outside the normal range will also be flagged in the data listings, along with corresponding normal ranges.

D. Vital Signs

Vital signs including sitting blood pressure (systolic and diastolic), heart rate, body temperature and respiratory rate will be presented in a by-subject listing by visit. Descriptive summaries of actual values and changes from Baseline will be calculated for vital signs by treatment group.

E. Electrocardiogram (ECG)

Descriptive statistics will be used to summarize ECG results (actual values and changes from Baseline) at Screening, Baseline (Day 1), and Day 169/Week 24. The incidence of abnormal ECG interpretation will be summarized.

All results will also present in a by-subject listing and abnormal ECG findings will be flagged.

F. Physical Examination

The frequency of subjects with abnormal evaluations of body system findings for physical examinations will be summarized by visit and treatment group. Abnormal physical examination findings will also be presented in a by-subject listing.

Any new findings of Clinically significant abnormalities in physical exam will be recorded as AEs.

G. Injection Site Assessment

The frequency of subjects with any injection site reaction will be summarized by visit and treatment group. Severity (0 to 4) of erythema (0=None, 1=Very Slight, 2=Slight, 3=Moderate, 4=Severe), drainage (0=None, 1=Serous, 2=Serosanguinous, 3=Bloody, 4=Purulent), edema (0=None, 1=Very Slight, 2=Slight, 3=Moderate, 4=Severe), induration (0=None, 1=Minimal, 2=Mild, 3=Moderate, 4=Severe), hematoma (0=None, 1=Minimal, 2=Mild, 3=Moderate,

4=Severe) will be summarized using frequency counts and percentages by visit and treatment group. Injection site reactions will be presented in a by-subject listing.

H. Other Safety Assessments

The frequency of subjects with positive anti-drug antibodies (ADA) will be summarized by visit and treatment group. Positive anti-drug antibodies (ADA) will also be presented in a by-subject listing.

10. Other Assessments

A. PK/PD Analyses

Pharmacokinetics: Individual plasma concentrations will be summarized using descriptive statistics by treatment and scheduled time if applicable or plotted on means overtime if appropriate. The PK analyses will be documented separately in the PK/PD SAP.

Pharmacodynamics: Changes of serum levels of IL-4, IL-13, IgE, TARC and Peripheral eosinophil count will be summarized using descriptive statistics by treatment and scheduled time and, if appropriate, plotted for each treatment together with mean and SD. The PD analyses will be documented separately in the PK/PD SAP. Details and results of the PK and PD analyses will be reported separately in the PK/PD Analytical Report and the PK/PD Report.

11. Changes from the Protocol and Planned Analyses

The following deviations or clarification from the protocol in planned statistical analyses are listed below, along with the justifications:

1. Addition of Week 20 timepoints in Secondary Efficacy Endpoints and Other Efficacy Endpoints in section Secondary Objectives:

This is to explore the treatment effect after 4 weeks off treatment.

2. The order of testing each CBP-201 group vs. placebo is changed in sections Multiple Comparisons and Multiplicity and Primary Efficacy Outcome Analysis

From:

1. After a 600 mg loading dose, 300 mg dose Q2W
2. After a 600 mg loading dose, 300 mg dose Q4W
3. After a 600 mg loading dose, 150 mg dose Q2W

To:

1. After a 600 mg loading dose, 300 mg dose Q2W
2. After a 600 mg loading dose, 150 mg dose Q2W
3. After a 600 mg loading dose, 300 mg dose Q4W

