¹⁵ AEs and SAEs will be collected starting from the time that the Informed Consent is signed. AEs and AEs of special interest (AESIs) will be collected at each study visit. During follow-up period beyond study completion or after an ET, only those SAEs considered to be related to study treatment should be reported.

¹⁶ Unscheduled or early termination (ET) visits may occur at any time. Unscheduled visits (UVs) may occur to assess AEs or disease progression, for example. It is left to Investigator discretion to determine what if any assessments are appropriate for an UV, however VS, physical examination, assessment of injection sites, query subject for any AEs and new concomitant medications or treatments at the minimum should be performed. UVs occurring after W24 may be scheduled to follow AEs to resolution or establishment of a new baseline (progression of AE has been stabilized) or for assessments regarding disease progression. After an ET, a visit should be scheduled promptly to determine the reason for ET and to perform study closeout assessments assuming the subject is willing to return to the clinic and undergo such procedures. Note that subjects who develop any CTCAE grade 2 or higher cardiovascular or respiratory TEAE or any grade 3 or higher TEAE involving other organ systems must be discontinued from further study treatment dosing and monitored until resolution or stabilization.

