10.4. Miscellaneous Safety Assessments

10.4.1. Clinical Laboratory Assessments

All protocol-specified laboratory tests on blood and urine samples will be performed at a central laboratory. Blood samples will be collected, processed, and shipped according to instructions from the central laboratory. Additional samples taken may be necessary to repeat testing following abnormal laboratory results or clinical symptoms necessitate testing to ensure safety at the discretion of the Investigator. Required assessments for blood tests are listed in [Table 4](#).

Table 4. Clinical Laboratory Assessments

Hematology	Chemistry	Urinalysis
Hematocrit Hemoglobin Red blood cell (RBC) count Total and differential (absolute) white blood cell count Platelet count	Sodium Potassium Chloride Carbon dioxide Glucose Total protein Albumin Creatinine Blood urea nitrogen (BUN) Total bilirubin Alanine aminotransferase (ALT) Aspartate aminotransferase (AST) Gamma-glutamyl transferase (GGT) Alkaline phosphatase	Urinalysis with microscopic analysis if abnormal

It is the responsibility of the Investigator to review and sign all lab reports expeditiously, and to document appropriate safety monitoring of study subjects. The Investigator should sign and date each lab report concurrent with her or his review, and should indicate the clinical significance of each abnormal/flagged value by noting “NCS” (not clinically significant) or “CS” (clinically significant), for example. Notations indicating that a value is clinically significant should also include a brief description of the underlying disease or condition that is associated with the value, e.g., “CS/mild anemia.” In general, and as determined by the investigator, abnormal, clinically significant laboratory values are expected to be associated with an item recorded in medical history or with an AE. The investigator may use the Common Terminology Criteria for Adverse Events (CTCAE) Version 5.0 (published November 27, 2017 and available at: https://ctep.cancer.gov/protocoldevelopment/electronic_applications/docs/CTCAE_v5_Quick_Reference_5x7.pdf) to assist in the determination of severity and clinical significance.

10.4.2. 12-Lead Electrocardiogram (ECG)

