Reduction from baseline will be defined as: $\text{Baseline value} - \text{post-Baseline value}$. The percent reduction from Baseline will be calculated as reduction from Baseline divided by the Baseline value, expressed as a percentage.

Change from Baseline is defined as: $\text{post-Baseline value} - \text{Baseline value}$. The percent change from Baseline will be calculated as change from Baseline divided by the Baseline value, expressed as a percentage.

Day 1 is defined as the date of first administration of study treatment. Study day is calculated relative to the date of Day 1.

C. Analysis Visit Window

Because all study medication will be administered at the study center via subcutaneous (SC) injection every 2 weeks, all efficacy and safety endpoints will be summarized and analyzed according to their nominal visit as assigned, except for ET visits. ET visits will be re-mapped to the last nominal visit number + 1. For example, if a subject attended Week 2, Week 4, Week 6 and then early terminated, the early termination visit will be re-mapped and analyzed as Week 8. No analysis visit window mapping based on actual study day will be performed other than that for ET visits.

Unscheduled visits will not be re-mapped and will not be included in table summaries. They will only be listed.

D. Multiple Study Centers

This study will be conducted by multiple investigators at multiple centers internationally. Descriptive summaries of the primary and secondary efficacy endpoints will be presented for each individual study center to evaluate potential heterogeneity across sites. Baseline characteristics and key safety endpoint may be presented for each study center as appropriate. The implications of any significant heterogeneity on the assessment of overall efficacy will be explored.

E. Covariate Adjustment in Primary Analysis

The primary efficacy analyses will adjust for baseline EASI score and baseline IGA score (moderate, severe) as described in Section 8 Efficacy Analyses below.

F. Subgroup Analysis

Exploratory subgroup analysis of the primary or other efficacy endpoints based on demographic factors or other covariates may be performed on an ad hoc basis, using descriptive statistics. Grouping factors may include:

- Age
- Sex
- Race
- Ethnicity
- Baseline IGA Score

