 - defined as the total number of AD flares with an onset date from baseline to Week 16. Number of AD flares will be summarized using descriptive statistics for each treatment group using OC. Number and percentage (along with the 95% CI) of subjects with at least one AD flare during each period will be provided for each treatment group.
- Number of subjects with AD flares from Baseline to Week 8 and from Week 8 to Week 16 and Week 20:
 - AD flares on Baseline to Week 8 and from Week 8 to Week 16 will be defined similarly by AE onset date as described above. AD flares that start before Week 8 and are ongoing or resolve after Week 8 will be counted in the first period (baseline to Week 8) only.
- Number of days with AD flares through Week 16:
 - the duration of each AD flare is defined as (resolution date of AE – onset date of AE + 1) among subjects with at least one AD flare. For subjects reporting more than one flare, the total subject-days of duration would be calculated and used in statistical summary. Details regarding calculation of duration of AE are described in section 9 below. Number of days with flares will be summarized using descriptive statistics for each treatment group.

All efficacy endpoints will be summarized for FAS using descriptive statistics or frequency counts and percentage for all scheduled visits, for each treatment group.

9. Safety Analyses

Safety analyses will use data from the Safety population. Safety data will be summarized using frequency tables (counts with percentages) and will be presented by treatment and scheduled visits if applicable. Continuous safety data will be summarized using descriptive statistics by treatment and scheduled visits. Data will be compared to the reference ranges provided and be checked for abnormality and/or clinically relevant changes from baseline, where applicable. No formal statistical comparisons will be performed for safety endpoints.

A. Exposure

The following exposure parameters will be defined and summarized by treatment group using descriptive statistics:

- Number and percentage of subjects receiving any injection of study drug at each visit
- Number of injections received at each visit and overall
- Volume (mL) of study drug injected at each visit and overall
- Dose (mg) of study drug injected at each visit and overall
- Number and percent of subjects that have dose interruptions, as well as those with dose interruptions due to AEs

B. Adverse Events

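### Lab values, vital signs and injection-site grades measured at unscheduled visits reach listings only, because SAP 5.C excludes them from tables and SAP 9 has no worst post-baseline summary

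*SAP*

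**What the plan says.** SAP 5.C (Analysis Visit Window) sets one rule for both kinds of endpoint: "all efficacy and safety endpoints will be summarized and analyzed according to their nominal visit as assigned, except for ET visits". Early-termination visits are re-mapped to the next nominal visit and so enter the tables. For unscheduled visits the rule is: "Unscheduled visits will not be re-mapped and will not be included in table summaries. They will only be listed". No exception is made for safety data.

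The opening of SAP 9 is consistent with this: "Safety data will be summarized using frequency tables (counts with percentages) and will be presented by treatment and scheduled visits if applicable". Within SAP 9:

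- **9.C, laboratory:** shift tables show how many subjects fall into each of three classes: "clinical laboratory parameters will be categorized as low, normal, or high according to laboratory range specifications". Out-of-range values are flagged in listings.
- **9.D, vital signs:** descriptive summaries of values and changes from baseline, plus a by-subject listing.
- **9.G, injection sites:** frequency of any reaction, and grades 0 to 4 for each of five parameters, by visit and treatment group.

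The protocol describes what unscheduled visits are for. Table 1, footnote 16: "Unscheduled visits (UVs) may occur to assess AEs or disease progression, for example". The same footnote makes vital signs, physical examination and injection-site assessment part of the minimum work-up there. Section 7.1.8 lists safety labs as something the investigator may consider. Section 10.4.1 adds: "Additional samples taken may be necessary to repeat testing following abnormal laboratory results or clinical symptoms".

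**The concern.** A visit outside the schedule is usually held for a reason, and assessing an adverse event is one that the protocol names. The values recorded there are more likely than routine ones to include a subject's extreme. A rule that keeps them out of by-visit rows is sensible, because they belong to no nominal time point. The same rule becomes a gap when no other table collects them.

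At stake is the tabulated evidence on labs, vital signs and injection-site grades, which supports the secondary objective on safety and tolerability. With four arms of about 55 subjects, a listing is a poor tool for comparing arms, even when abnormal values are flagged.

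**Working it through.** No calculation applies. The plan states no figure on this point, and the question is which data enter which table. The check sets the sections side by side.

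**Step 1: does the exclusion reach safety data?** Yes. SAP 5.C names safety endpoints in its opening sentence, and the unscheduled-visit sentence carries no restriction.

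**Step 2: does any part of SAP 9 bring the values back?** No. Only 9.G says expressly that its tables are by visit; 9.C and 9.D take that layout from the general sentence at the start of SAP 9. The layout does not decide the matter. Even if the 9.C shift tables were programmed across visits, 5.C would still keep unscheduled results out of them. Sections 9.C, 9.D and 9.G define no worst or any-time post-baseline category.

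**Step 3: are such values likely to be collected?** Vital signs and injection-site assessments are, by footnote 16. Labs may be: Table 1 has no mark for safety labs in the unscheduled column, but 7.1.8 and 10.4.1 allow them at the investigator's discretion. Post-dose safety labs are otherwise scheduled only at W2, W4, W8, W16 and W24, plus early termination.

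**Step 4: where does each finding end up?**

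| Post-dose finding at an unscheduled visit | Visit-based table | AE table | Listing |
|---|---|---|---|
| Lab value recorded as an AE | No | Yes: term and severity | Yes; flagged if out of range |
| Out-of-range lab value not recorded as an AE | No | No | Yes, flagged |
| Vital-sign value | No | Only if recorded as an AE | Yes |
| Injection-site grades per parameter | No | Only as an AE, if clinically significant; not by parameter | Yes |

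The AE column rests on protocol 11.1.4 (conditions for recording lab, vital-sign and ECG abnormalities), Table 1 footnote 14 and 13.7.3 (injection sites), and SAP 9.B, whose tables are organised by subject and event, not by visit.

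**Illustration.** A subject has a normal liver enzyme at W8 and W16 and a high value at an unscheduled draw between them. If no AE is recorded, the lab shift table shows normal at both visits and the high value is in the listing alone. If an AE is recorded, the AE table shows the term and severity, but the shift table is unchanged.

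**Step 5: is this a declared change?** Protocol 13.7.1 plans lab statistics at each assessment time, and shift tables, with no exclusion of unscheduled visits. SAP 11 lists changes to the Week 20 time points, the testing order and the imputation method. It does not mention this exclusion.

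**The case against.** The strongest reply is that the AE tables already do this work. The conditions in protocol 11.1.4 include accompanying symptoms, further diagnostic testing, intervention and a change in dosing. Values that lead to an unscheduled visit are the ones most likely to meet them, and SAP 9.B tabulates treatment-emergent AEs by maximum severity, with an injection-site-reaction line in the overview. This stands, and it narrows the gap. A reader might infer from 5.C that everything found at an unscheduled visit disappears from every safety table; SAP 9.B shows that this is not so. It does not close the gap: an AE row carries neither the measured value nor its shift from baseline nor the grade per parameter, and some abnormalities will not be recorded as AEs.

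Other points also stand:

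- Section 10.4.1 does not tie repeat samples to unscheduled visits. Subjects attend every two weeks through W16 and five times afterwards, and a repeat drawn at a scheduled visit is outside the exclusion.
- Vital signs are taken at every scheduled visit. Injection sites are checked at every dosing visit and at W17 and W20.
- Protocol 13.7.3 planned only listings for injection-site data, so the SAP already goes further than the protocol there.
- Scheduled-visit tables keep the number of assessments similar across arms. That is a good reason to leave them as they are, though not a reason to have no other summary.

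A reader might also infer that the low, normal and high categories conflict with a CTCAE grading requirement for labs. They do not: the categories come from protocol 13.7.1, and sections 10.4.1 and 11.1.2 offer CTCAE to investigators only as an aid.

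**Conclusion.** The gap is real but limited. Values and Appendix H grades measured at unscheduled post-dose visits enter no visit-based safety table, and abnormalities found there and not reported as AEs enter no table at all. Nothing is lost from the database or the listings.

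The size cannot be stated. The documents do not give the number of unscheduled visits or of labs drawn at them. A reader might try to estimate it from the two 56-day gaps between scheduled labs (D57 to D113, and D113 to D169). Those gaps show how sparse the lab schedule is, not what 5.C removes: an abnormality that nobody measures is missed under any table rule.

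A reader might also infer that the tables flatter CBP-201. The documents do not support a direction. Unscheduled visits also serve disease progression and assessments before rescue treatment, including safety labs (protocol 7.1.2.3), and protocol 13.6.2 expects placebo subjects to need rescue topical steroids more often or for longer. Nor are the worst observations always omitted; that happens only when the extreme falls at an unscheduled visit.

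The conclusion rests on reading 5.C as written. It concerns post-dose values only, since a pre-dose unscheduled result could serve as baseline under SAP 5.B.

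**What to change.** 1. In SAP 5.C, limit the unscheduled-visit exclusion to efficacy tables and by-visit rows of safety tables.
2. In SAP 9.C, add a shift table from baseline to worst post-baseline value, with low and high directions shown separately.
3. In SAP 9.D, add worst post-baseline values for each vital sign.
4. In SAP 9.G, add the worst post-baseline grade for each injection-site parameter.
5. Base items 2 to 4 on all post-baseline results: scheduled, unscheduled and early-termination. Leave the by-visit tables unchanged.

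The cost is some SAP wording and a few extra tables from data already collected; no efficacy analysis changes. The downside is uneven ascertainment. Subjects with symptoms or needing rescue, possibly more often on placebo, are assessed more often and so have more chances of an extreme value, which could blur a true difference between arms. Each new table should carry a footnote saying so and be read beside the scheduled-visit tables.

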13.2. Sample Size Justification

The first primary efficacy endpoint is percentage of reduction of EASI at week 16. While the final analysis is planned to be analysis of variance (SAS[®] PROC MIXED for ANOVA) with confounding covariates, for simplicity, the sample size is calculated using a simpler 2-sample independent t-test. Based on the preliminary results at week 4 and more empirical data, the following input parameters were used for power and sample size calculation:

Parameters:

- Type I error (α) = 0.05 (two-sided)
- The non-inferiority margin of 35% between the CBP-201 300 mg Q2W vs. Placebo
- Common standard deviation (σ) = 45%
- Effective sample size: 44 per arm, after considering of 20% dropout rate from 55 randomized per arm

Hypotheses:

$$H_0: \Delta_{\text{CBP-201-300 mg Q2W} - \text{Placebo}} = 0$$

$$H_1: \Delta_{\text{CBP-201-300 mg Q2W} - \text{Placebo}} \neq 0$$

Statistical test: Two-sample t-test for mean difference

Based on method described above, a sample size of 220 (55 per arm, or effective sample size of 44 per arm considering 20% dropout rate) will provide 95% power to detect the treatment effect on the primary endpoint between the CBP-201 300 mg Q2W vs. Placebo.

To further detect the other treatment effects vs. Placebo, and also preserve the alpha at 0.05 level, a hierarchical multiple testing procedure is adopted, from the highest dose (300 mg Q2W) to the lowest dose (150 mg dose Q2W), until statistical significance at 0.05 level is not achieved.

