Study subjects are adults between 18 and 75 years old (both included) at the screening visit (Screening) with AD (according to American Academy of Dermatology Consensus Criteria, Eichenfield 2014) present for at least 1 year prior to the baseline visit (Baseline). In terms of AD, subjects must have an inadequate response to AD treatment with a topical regimen of corticosteroids, phosphodiesterase inhibitors or calcineurin inhibitors, or for whom topical treatments are otherwise medically inadvisable, and have IGA score ≥ 3 , EASI score ≥ 16 , and BSA for total AD involvement $\geq 10\%$ at Screening and Baseline.

C. Sample Size Determination

A sample size of 220 (55 per arm, providing approximately 44 completers per treatment group assuming 20% dropout rate) will provide 95% power to detect at treatment effect on the primary endpoint of percentage reduction of EASI at week 16 between the CBP-201 300 mg Q2W vs. Placebo. This power calculation

is based on the use of a two-sided two-sample t test at the $\alpha=0.05$ level of significance. Based on the preliminary results at Week 4 and empirical data, the mean between-group difference is assumed to be equal to 35 percentage points and the pooled standard deviation is assumed to be 45% using 2-sample independent t-test.

D. Treatment Randomization

Patients will be randomized at a 1:1:1:1 ratio into the following 4 groups: CBP-201 1800 mg (600mg load D1 then 150 mg Q2W), CBP-201 3000 mg dose (600mg load D1 then 300 mg Q2W), CBP-201 1800 mg dose (600mg load D1 then 300 mg Q4W), or placebo, respectively. The randomization is not stratified.

E. Assessment Schedule

The date at which the subject is randomized will be referred to as the “Baseline/Day 1” visit. Subjects will be requested to attend the scheduled visits for the Treatment Period every 2 weeks from their Baseline/Day 1 visit through Week 16. The acceptable visit window for scheduled visits during the Treatment Period is ± 2 days. After Week 16 of treatment, subjects will no longer receive any treatments but will return for an additional 8 weeks for follow-up visits. The acceptable visit window for scheduled visits during the Follow-up Period is ± 3 days.

In the case of an early termination (ET) from the study for any reason, study completion assessments should be performed as detailed for the study completion visit and should be completed within 7 days of the ET, whenever possible.

F. Clinical Trial Material

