In addition, exploratory subgroup analysis of EASI-100 (proportion of subjects achieving 100% reduction of EASI score from baseline), proportion of ≥ 3 -point and ≥ 4 -point reduction in weekly average of PP-NRS at Week 16 will be performed using similar method as described for binary secondary efficacy endpoints (IGA response, EASI-50, 75, 90 response), among subjects enrolled in China. Other exploratory subgroup analysis of efficacy or safety endpoints may also be performed among subjects enrolled in China on an ad hoc basis. No formal statistical comparison will be performed.

G. Interim Analyses

No formal interim analysis of efficacy is planned.

H. Multiple Comparisons and Multiplicity

The primary efficacy endpoint will be analyzed using the analysis of covariance (ANCOVA) statistical method. Pairwise comparisons for each CBP-201 group vs. placebo will be performed and a serial gatekeeping procedure will be used for multiplicity adjustment. From the highest dose (300 mg Q2W) to the lowest dose frequency (300 mg dose Q4W), each CBP-201 group will be compared with the placebo group in order, until statistical significance at 0.05 level is not achieved. This procedure helps preserve the alpha at 0.05 level.

I. Analysis Populations

The following analysis populations will be defined for the study:

Table 1. Analysis Populations

Analysis Populations	Description
Screened	All Subjects Screened (Screened) set will contain all subjects who signed informed consent.
Randomized	All Randomized Set (Randomized) will contain all subjects who are randomized into the study, no matter whether they were treated or not.
Safety Set (SS)	The SS will include all randomized subjects who received at least part of an SC dose of study treatment.
PK Set (PKS)	The PKS will include all randomized subjects who received at least 1 dose of active study treatment and have at least 1 PK sample collected and analyzable.
Full Analysis Set (FAS)	The FAS will include all randomized subjects who received at least part of an SC dose of study treatment.
Per Protocol Set (PPS)	The PPS will contain a subset of FAS subjects who do not have any major protocol deviations that could influence the validity of the data for the primary endpoint. A subject may be excluded from the PPS if any of the following criteria (but not limited to) are met:

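### Subjects enrolled in China are a named subgroup, but the primary model has no region term and the SAP commits to no China estimate of the primary endpoint

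*SAP*

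**What the plan says.** - **Randomisation.** SAP 4.D gives 1:1:1:1 allocation and adds: "The randomization is not stratified".
- **Primary model.** SAP 5.E: "The primary efficacy analyses will adjust for baseline EASI score and baseline IGA score (moderate, severe". The code in SAP 8.B has treatment, baseline IGA and baseline EASI, with no term for region, country or centre.
- **Country.** SAP 6.A lists it as a baseline characteristic to be summarised. It appears in no efficacy model, and it is not among the general subgroup factors in SAP 5.F (age, sex, race, ethnicity, baseline IGA), which are themselves optional.
- **Committed China analyses.** SAP 5.F commits to "exploratory subgroup analysis of EASI-100 (proportion of subjects achieving 100% reduction of EASI score from baseline"), and to the proportions with at least a 3- and a 4-point fall in weekly PP-NRS at Week 16. All three are Other Efficacy Endpoints in SAP 3.C.
- **Everything else in China.** "Other exploratory subgroup analysis of efficacy or safety endpoints may also be performed among subjects enrolled in China on an ad hoc basis". The same section rules out formal comparison.
- **Centres.** SAP 5.D commits to descriptive summaries of the primary and secondary endpoints for each centre, and to exploring what any heterogeneity implies for overall efficacy.
- **Changes from protocol.** SAP section 11 lists three items. None concerns region or China.

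**The concern.** The SAP treats enrolment in China as worth a separate look, and records country, but uses it neither in the design nor in the primary model. If outcome differs by region for reasons not captured by baseline EASI and IGA, a chance difference in regional mix between two arms stays in the estimate. The protocol offers a reason to think this possible. Its section 5.1 contrasts two-thirds of AD presenting by age 2 with a Chinese hospital series in which 77.5% had onset after age 12. That makes a difference plausible; it does not show that response differs.

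The second half matters more. A reader who sees a China subgroup will first ask whether the main effect holds there. The plan commits to three responder endpoints but not to the primary endpoint, IGA 0-1 or EASI-75. Whether those are shown for China is left open, so a later China result on them could not be called prespecified.

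**Working it through.** **Inputs from the documents.** Protocol 13.2: "Type I error (α) = 0.05 (two-sided"). SAP 4.C: the calculation "is based on the use of a two-sided two-sample t test at the" 0.05 level; "the mean between-group difference is assumed to be equal to 35 percentage points and the pooled standard deviation is assumed to be 45" percent; "A sample size of 220 (55 per arm, providing approximately 44 completers per treatment group assuming 20% dropout rate"). Protocol synopsis: about 60 sites.

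**Inputs assumed.** The documents give neither the China share p nor the difference g in mean EASI reduction between China and elsewhere. I take p = 20% to 40% and g = 10 to 20 percentage points, and show a wider range where it helps.

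**1. The plan's own figure.** SE = 45 × √(2/44) = 9.59. Noncentrality = 35/9.59 = 3.65 on 86 df. Power = 95.0% (95.4% by normal approximation). 44/0.80 = 55 per arm, and 4 × 55 = 220. The stated figures reproduce.

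**2. Chance imbalance, 55 per arm.** SD of the between-arm difference in China share = √(2p(1−p)/55), which is 0.076 at p = 20% and 0.093 at p = 40%. Multiplying by g gives the SD of the resulting shift in the contrast:
- p = 20%: 0.8 to 1.5 points (95% range ±1.5 to ±3.0)
- p = 40%: 0.9 to 1.9 points (95% range ±1.8 to ±3.7)

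The SE of the contrast is 45 × √(2/55) = 8.58, and the assumed effect is 35.

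**3. Precision gained from a region term.** Share of variance removed = p(1−p)g²/45², reading 45 as the total SD. Power uses 44 per arm.

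| p | g | Variance removed | Residual SD | Power |
|---|---|---|---|---|
| 20% | 10 | 16/2025 = 0.8% | 44.8 | 95.2% |
| 20% | 20 | 64/2025 = 3.2% | 44.3 | 95.6% |
| 40% | 10 | 24/2025 = 1.2% | 44.7 | 95.2% |
| 40% | 20 | 96/2025 = 4.7% | 43.9 | 95.9% |

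At p = 50% and g = 30 the residual SD is 42.4 and power 96.9%. The required N does not change. Baseline EASI and IGA are already in the model, so any part of g that runs through severity is already removed.

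**4. Type I error.** A simulation of the unadjusted test used 40,000 trials per setting, 44 per arm, p = 20% or 50%, g = 20 or 30 and no treatment effect. It rejected in 4.8% to 5.1% of trials, and the mean difference was within 0.1 point of zero.

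**5. What a China estimate would look like.** Half-width of the 95% CI = t × 45 × √(2/m) for m per arm. With m = 10: 2.101 × 20.12 = 42.3 points. With m = 5 it is 66 points, and with m = 15 it is 34. Power for a 35-point difference at m = 10 is 38%. This can only be an estimate with an interval.

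**6. The committed China endpoints.**
- EASI-100 will be sparse. At an assumed rate of 5% to 15%, 10 per arm gives 0.5 to 1.5 expected responders.
- For the itch responders, protocol 5.4.2 (the earlier multiple-dose study, Day 29) gives 4/7 on 300 mg against 2/8 on placebo for a fall of more than 3 points. It gives 3/7 against 1/8 for IGA 0-1. At those rates, Fisher exact power with 10 per arm is about 15% for each.

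**7. The per-centre summaries.** 220/60 = 3.7 subjects per site, or 3.7/4 = 0.9 per arm per site.

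**The case against.** Unstratified randomisation is valid, and chance imbalance is already in the standard error. Step 4 confirms this. Two severity covariates are a legitimate choice for a Phase 2 trial. The SAP defines no region, and China/other would pool every other country. The gain is under one percentage point of power in the main range, and nothing in the documents shows that region is prognostic. The China analyses are declared exploratory, so no claim depends on them, and SAP 5.D already commits to primary and secondary results by centre.

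Most of this stands. It removes three stronger readings that a reader might infer:

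- **That the primary contrast is biased or its alpha inflated.** It is not. The effect is on precision and conditional balance only.
- **That the China result rests on the least informative endpoint.** It does not. EASI-100 is sparse, but the itch responders are committed too. On the earlier study's rates (small samples, Week 4, a slightly different itch threshold) they carry about as much information as IGA 0-1.
- **That the SAP plans nothing on the main endpoints that bears on heterogeneity.** The per-centre summaries are committed output and include IGA 0-1 and EASI-75.

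What does not stand is that the centre tables fill the gap. With under one subject per arm per site they give no pooled China effect. Low power is no reason to omit the estimate either, since an exploratory subgroup is read by its interval.

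**Conclusion.** The point holds as a minor improvement. The primary model omits a baseline factor that the SAP collects and singles out, and the primary endpoint in the one country subgroup it names is left to ad hoc choice.

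The loss from the first part is small: about 1% to 5% of residual variance for a China share of 20% to 40% and a regional difference of 10 to 20 points. Both ranges are assumed, and the figure is lower if part of that difference runs through severity. The validity of the primary test is not in question.

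The second part needs no assumption: the SAP promises no pooled China estimate of the main effect. The documents do not suggest that selective reporting is intended; they only leave the choice open.

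**What to change.** 1. **SAP 5.E and 8.B.** Add region (China / other) as a fixed factor in the primary ANCOVA, and keep the current model as a sensitivity run. If the sponsor prefers not to change the primary model, prespecify the region-adjusted model as a sensitivity analysis. Settle this before unblinding and record it in SAP section 11.
2. **SAP 5.F.** Add the primary endpoint to the committed China analyses, as the adjusted difference from placebo with a 95% CI for each regimen. Summarise IGA 0-1 and EASI-75 descriptively. Keep EASI-100 and the itch responders, and label the set exploratory.

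The cost is one degree of freedom, some SAP wording and a few tables. Randomisation, sample size and conduct do not change. The drawback is wide China intervals (half-width about 42 points with 10 per arm), which the report should state so that they are not read as a test of effect in China.
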